2.4.2 Primary Effectiveness Endpoint (each substudy)

Treatment success: Technical success (defined as successful access and deployment of all required CEXC Device components) and freedom from the following events:

- Type I endoleaks in the 12 month analysis window
- Type III endoleaks in the 12 month analysis window

- Migration ≥ 10 mm between the baseline and the 12 month analysis window
- AAA enlargement ≥ 5 mm with or without intervention between the baseline and the 12 month analysis window
- AAA rupture through the 12 month analysis window
- Conversion to open repair through the 12 month analysis window

The baseline assessment shall occur prior to the end of the one month study window for the Short Neck Substudy and within the first 90 post-operative days for the High Neck Angulation Substudy.

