2.5.2 Primary Effectiveness Endpoint (each substudy)

The analysis of the primary effectiveness endpoint is intended to test the hypothesis that the effectiveness of the CEXC Device exceeds the performance goal of 80% freedom from effectiveness endpoint events in each substudy separately.

[figure not shown]
The hypotheses are specified as follows:

$$H_0: P_{EE} \le 0.80$$

 $H_A: P_{EE} > 0.80$

Doc Type: GC

2.6 Sample Size Assumptions For the Short Neck Substudy primary safety endpoint, a one sided test with alpha = 0.05, For the High Neck Angulation Substudy primary safety endpoint, one sided test with alpha = 0.05, For the Short Neck Substudy primary effectiveness endpoint, one sided test with alpha = 0.05, For the High Neck Angulation Substudy primary effectiveness endpoint, one sided test with alpha = 0.05, 2.7 Sample Size Calculations 80 Subjects will be utilized in the Short Neck substudy. The High Neck Angulation substudy sample size of 95 Subjects will be utilized.

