5.0 Statistical Analyses

5.1 Analysis Populations

The following populations will be used in various analyses of the data collected in the AAA 13-03 study:

- 1. All Enrolled Subjects This population will consist of all enrolled Subjects
- Safety Eligible Population (each substudy) This population will consist of Initial Cohort Subjects with a follow-up visit at or after 30 days following initial CEXC Device implant procedure. Additionally, any Subjects with an eligible safety event, as defined in Section 2.4.1, even if they did not complete a follow-up visit at or after 30 days following initial procedure, will be included.

3. Primary Effectiveness Population

Short Neck Substudy - This population will consist of Initial Cohort Subjects with both post-op (no later than one month study window) contrast-enhanced CT imaging and a 12 month follow-up visit that included contrast-enhanced CT imaging. Additionally, any Subjects with an eligible effectiveness event, as defined in **Section 2.4.2**, even if they did not complete the necessary follow-up visit or imaging to otherwise be included in the population, will be included.

High Neck Angulation Substudy – This population will consist of Initial Cohort Subjects with both post-op (no later than 90 days) contrast-enhanced CT imaging and a 12 month follow-up visit that included contrast-enhanced CT imaging. If a subject without a 12 month contrast-enhanced CT imaging has post-12 month contrast-enhanced CT imaging at which there was no endpoint event identified by Core Lab (Type I Endoleak, Type III Endoleak, Migration, or Rupture) using the post 12-month contrast CT closest to the 12-month window, the subject will also be included in the analysis. Additionally, any Subjects with an eligible effectiveness

event, as defined in **Section 2.4.2**, even if they did not complete the necessary follow-up visit or imaging to otherwise be included in the population, will be included.

Secondary Effectiveness Populations (each substudy, each endpoint) - These
populations will consist of Initial Cohort Subjects with an evaluable result for the
specific variable.

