5.4 Statistical Analysis of Endpoints

One-sided exact Clopper-Pearson confidence intervals for binomial proportions (alpha=0.05) will be constructed to test the primary safety and primary effectiveness hypotheses in each substudy. The null hypothesis will be rejected if the lower bounds of the 95% confidence interval estimating device effectiveness and safety exceeds the performance goal. This is equivalent to stating that the estimated effectiveness and safety must exceed the PG with a Type I error rate (alpha) of < 0.05.

All events must meet the protocol definition and will be adjudicated through the CEC process.

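### Entry into the Primary Effectiveness Population depends partly on outcome, so the direction of bias is undetermined and the stated type I error below 0.05 is not guaranteed

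*SAP*

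**What the plan says.** **Entry (SAP 5.1, item 3).** In both substudies a subject enters with a post-operative contrast CT and "a 12 month follow-up visit that included contrast-enhanced CT imaging". A subject with an eligible effectiveness event also enters "even if they did not complete the necessary follow-up visit or imaging to otherwise be included in the population, will be included". In High Neck Angulation only, there is a third route. A subject without the 12-month CT is admitted if the nearest later contrast CT shows no Type I or III endoleak, migration or rupture. Enlargement and conversion are not on that list.

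**Endpoint (SAP 2.4.2).** The endoleak components are limited in time: "Type I endoleaks in the 12 month analysis window", and likewise for Type III. SAP 4.2 sets that window at days 243 to 546. Rupture and conversion count at any time up to its end. Migration and enlargement are counted from baseline to that window. Technical success is stated separately from the list of events.

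**Unsuccessful implants (SAP 2.1).** A subject given another stent graft at the index procedure, without implantation of the study device, is tracked for 30 days only.

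**Test (SAP 5.4, 2.5.2, 2.7).** "One-sided exact Clopper-Pearson confidence intervals for binomial proportions (alpha=0.05) will be constructed". The device "must exceed the PG with a Type I error rate (alpha) of < 0.05". The hypothesis is that effectiveness "exceeds the performance goal of 80% freedom from effectiveness endpoint events in each substudy separately". SAP 2.7 states that "80 Subjects will be utilized in the Short Neck substudy", and gives 95 for High Neck Angulation.

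**The concern.** An exact binomial bound holds its error rate for the enrolled population if subjects enter the denominator without regard to outcome. Here a known failure enters with any follow-up, while a subject with no known event generally needs the 12-month scan. That pushes the observed success rate down.

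Two features push it up:

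- **(a) Unseen failures.** Endoleak and migration, and mostly enlargement, cannot be seen without the CT. A subject who fails on one of these and misses the scan leaves the denominator. A subject whose only finding is an endoleak at 1 or 6 months, and who then dies, withdraws or misses the scan, has no eligible endoleak event and also leaves. Technical failures may leave too: with 30 days of tracking they would normally have no 12-month CT, and it is unclear whether technical failure is an eligible event.
- **(b) The High Neck late-CT rule.** A clean late scan enters as a success. A late scan with an endoleak, migration or rupture is not admitted by that rule. An endoleak first seen after day 546 is not an eligible event under SAP 2.4.2 either.

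Each substudy is declared successful on this bound together with the safety bound (SAP 1.1), and there is no control arm in which a similar bias could offset it.

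**Working it through.** **Inputs from the documents.** Goal 0.80; one-sided exact Clopper-Pearson bound, alpha 0.05; N = 80 and 95.

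**Inputs assumed (the documents give none).**
- ms, mf: probability that a success or a failure lacks the 12-month CT.
- c: share of those failures kept by the event clause.
- q: share of those successes admitted by a clean late CT (High Neck only; otherwise 0).

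**Step 1. The plan's own figure.** With every subject evaluable, the smallest passing counts are 71/80 (lower bound 0.812) and 83/95 (0.803). At a true rate of 0.80 the chance of passing is 0.0287 and 0.0424. Both are below 0.05, as the SAP states.

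**Step 2. Null success rate among evaluable subjects.** With true success 0.80:

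p* = 0.8[1 − ms(1 − q)] / {0.8[1 − ms(1 − q)] + 0.2[1 − mf(1 − c)]}

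p* exceeds 0.80 only if mf(1 − c) > ms(1 − q). Type I error is then summed over the random evaluable n, with the cut-off recomputed at each n.

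**Step 3. Event clause alone (ms = mf, q = 0).** With 10% missing and c = 0.5, p* = 0.72/(0.72 + 0.19) = 0.791 and type I error is 0.023 in both substudies. With 25% missing and c = 1 it is 0.0035 (N=80) and 0.0026 (N=95). The clause is conservative.

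**Step 4. Failures miss the CT more often (ms = 10%, mf = 20%, q = 0).**

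| c | p* | N=80 | N=95 |
|---|---|---|---|
| 0 | 0.72/(0.72 + 0.16) = 0.818 | 0.076 | 0.080 |
| 0.25 | 0.72/(0.72 + 0.17) = 0.809 | 0.052 | 0.054 |
| 0.5 | 0.72/(0.72 + 0.18) = 0.800 | 0.035 | 0.036 |

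**Step 5. The same question with a fixed number dropped.** Let 10 of 95 be dropped with success rate s. The other 85 then have rate (0.80 × 95 − 10s)/85 = (76 − 10s)/85, and 75/85 is needed to pass.

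| s | Rate in the 85 | Chance of passing | Failures dropped | Successes dropped |
|---|---|---|---|---|
| 80% | 0.800 | 3.3% | 2/19 = 10.5% | 8/76 = 10.5% |
| 70% | 0.812 | 5.8% | 3/19 = 15.8% | 7/76 = 9.2% |
| 60% | 0.824 | 9.6% | 4/19 = 21.1% | 6/76 = 7.9% |
| 50% | 0.835 | 15.2% | 5/19 = 26.3% | 5/76 = 6.6% |

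**Step 6. High Neck late-CT rule, equal missingness (N=95).** With ms = mf, p* exceeds 0.80 when q > c. At q = 0.8 and c = 0.25:
- 5% missing: 0.048
- 10% missing: p* = 0.784/(0.784 + 0.185) = 0.809, type I error 0.054
- 15% missing: 0.069
- 20% missing: p* = 0.768/(0.768 + 0.170) = 0.819, type I error 0.086

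At q = c = 0.5 it stays at about 0.036.

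**Step 7. What a tipping point would show.** Suppose 75/85 is observed (lower bound 0.809, a pass) and 10 subjects are unknown. Two failures among the 10 give 83/95 (0.803, still a pass). Three give 82/95 (0.791, a fail).

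**The case against.** A reader might infer that the exact test simply loses its error rate, or that subjects whose earlier CTs showed failure are dropped. The documents support neither.

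- The event clause lowers type I error (Step 3). Exceeding 0.05 needs failures to be lost sufficiently more often than successes, or the late-CT rule to recover enough successes.
- Rupture and conversion before the end of the window are always kept. Earlier migration or enlargement may be kept, depending on how SAP 2.4.2 is read; SAP 5.2 takes enlargement from the measurement nearest day 365 without naming a window.
- An endoleak seen only at 1 or 6 months is not an endpoint failure under SAP 2.4.2, even in a fully imaged subject. The protocol summary lists endoleak without a window, but the SAP definition governs this test.
- The larger figures in Step 5 need failures to be dropped about 2.7 to 4 times as often as successes. At s = 70% the excess over 0.05 is small. The window is wide, so few scans may be missed.
- The late-CT rule has a rationale: a clean later scan suggests a clean 12-month state, whereas an event on a later scan may have arisen after 12 months.
- The parts of SAP 5.5 before 5.5.5 are not visible, so a sensitivity analysis may already exist.

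All of this stands and limits the claim. It leaves the outcome-dependent entry in place. The rationale for the late-CT rule explains the asymmetry but does not remove its effect on the denominator.

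**Conclusion.** The point holds in limited form. Entry depends partly on outcome, the net direction of bias cannot be determined from the documents, and a type I error "with a Type I error rate (alpha) of < 0.05" is therefore not guaranteed for effectiveness in the enrolled population. It is not shown to be exceeded.

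Across the scenarios worked here, type I error runs from about 0.003 to 0.15 on either side of the nominal 0.05. Which side applies turns on whether mf(1 − c) exceeds ms(1 − q), and every one of those quantities is an assumption. The High Neck late-CT rule deserves most attention, because it can raise the error even when successes and failures miss the 12-month CT equally often. Whether the plan lacks a sensitivity analysis cannot be asserted.

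**What to change.** 1. **SAP 5.1, High Neck late-CT rule.** Make it independent of outcome: use the nearest post-12-month contrast CT whatever it shows, assess it for all imaging components including enlargement, and count an event there as a failure. This is somewhat strict, since such an event may postdate 12 months.
2. **SAP 5.1 or 2.4.2.** State that technical failure is an eligible effectiveness event.
3. **SAP 5.4.** Otherwise keep the present primary test, and add one supportive analysis per substudy with all Initial Cohort subjects in the denominator. Known failures under SAP 2.4.2 count as failures. For the remaining unknowns, report how many failures among them bring the lower bound to 80%, and the result with all of them failed. Show separately the result when an unresolved Type I or III endoleak on the last CT is counted as a failure, because that goes beyond the SAP definition. Report this next to the success statement.

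If the unseen parts of SAP 5.5 already contain such an analysis, only items 1 and 2 and the link to the success statement remain.

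Counting every unknown as a failure should not become the primary rule. At an assumed true success of 95%, power (Short Neck / High Neck) would fall from 0.993 / 0.999 with none missing to 0.749 / 0.867 at 5% missing and 0.259 / 0.367 at 10%.

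The cost is SAP wording, one extra table from data already collected, and possibly a slightly less favourable figure.

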4.0 Study Data Collection

4.1 Study Data Collection Intervals

Subjects will be asked to return for follow-up visits at one (1), six (6), 12, 24, 36, 48, and 60 months post-treatment. At each follow-up visit, subjects will undergo an evaluation for adverse events. Evaluation methods will include a physical examination and spiral CTA of the abdomen and pelvis (non-contrast and contrast spiral CTA required at one (1) month visit) (**Table 1**).

Table 1. Subject Schedule of Events

Diagnostic Test	Pre- treatment	Treatment	1 month	6 months	Annually for 5 years
Physical examination	Х		X	X	X
Creatinine concentration	Х				
Spiral computed tomography (contrast)	х		Х	X	Х
Spiral computed tomography (non contrast)			Х		
Angiography		Х			

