5.4.2 Primary Effectiveness Endpoint Events

Primary effectiveness endpoint events in each substudy will consist of all enrolled Subjects experiencing an event meeting the definition in **Section 2.4.2**.

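### High Neck Angulation effectiveness population: a late CT can bring a subject in as a success, but on the four screened findings never as a failure

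*SAP*

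**What the plan says.** SAP 5.1 gives a High Neck Angulation subject three ways into the Primary Effectiveness Population:

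1. A post-operative contrast CT by 90 days and a 12-month visit with contrast CT.
2. No 12-month contrast CT, but a later one "at which there was no endpoint event identified by Core Lab (Type I Endoleak, Type III Endoleak, Migration, or Rupture"). The rule continues: "using the post 12-month contrast CT closest to the 12-month window, the subject will also be included in the analysis".
3. An eligible effectiveness event under SAP 2.4.2, whatever imaging is missing.

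The Short Neck population in the same section has routes 1 and 3 only. Its imaging condition is "no later than one month study window) contrast-enhanced CT imaging and a 12 month follow-up visit that included contrast-enhanced CT imaging".

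SAP 2.4.2 ties each of the four screened findings to the 12-month analysis window. Two examples are "Type I endoleaks in the 12 month analysis window" and "AAA rupture through the 12 month analysis window". Table 2 in SAP 4.2 sets that window at days 243 to 546. SAP 5.4.2 says that primary effectiveness events "will consist of all enrolled Subjects experiencing an event meeting the definition in" Section 2.4.2. SAP 5.4 tests the 80% goal with a one-sided exact Clopper-Pearson bound and states a type I error below 0.05.

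**The concern.** Take a subject with no 12-month CT whose next contrast CT is after day 546. If that scan is clean, route 2 admits the subject. If it first shows a Type I or III endoleak, migration or rupture, route 2 is closed. Route 3 is closed too, because the finding falls outside the window in 2.4.2, and 5.4.2 counts nothing beyond 2.4.2. The subject leaves the denominator unless a different eligible event brings them in. On these four components, a late scan counts only when it is favourable.

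The exact test keeps its error rate only if entry to the denominator does not favour successes. This is the primary effectiveness test of the substudy, and SAP 1.1.2 requires it to be met for substudy success.

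**Working it through.** **Inputs from the SAP.** N = 95 (2.7); goal 0.80 (2.5.2); one-sided alpha 0.05 (2.6); reject if the Clopper-Pearson lower bound exceeds 0.80 (5.4).

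**The plan's own figure.** For x successes in n, the lower bound is the 5% quantile of Beta(x, n − x + 1). The smallest passing count at n = 95 is 83 (bound 0.8034). At a true rate of 80%, P(X ≥ 83) = 0.0424, which agrees with the stated error below 0.05.

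**Model of the entry rule.** These inputs are assumptions; the documents give none of them.
- m: subjects with no 12-month CT but with a later one.
- q: share of their 12-month failures dropped because of a finding on the late CT.
- r: share of their 12-month successes dropped because of a finding that arose after the window.

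With true rate p, the success share among late-CT subjects who enter is

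p(1 − r) / [p(1 − r) + (1 − p)(1 − q)],

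which exceeds p exactly when q > r. At p = 0.8, q = 0.5, r = 0.1 it is 0.72 / (0.72 + 0.10) = 0.878.

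**Type I error.** Let s late-CT subjects enter as successes and f as failures, so that n = 95 − m + s + f, and let c(n) be the smallest passing count. Sum over (s, f) the multinomial probability times P(Bin(95 − m, 0.8) ≥ c(n) − s). With m = 0 the result is 4.2%.

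| | q = 0.25 | q = 0.5 | q = 1 |
|---|---|---|---|
| m = 5, r = 0 | 4.8% | 5.2% | 6.1% |
| m = 10, r = 0 | 5.2% | 6.1% | 8.0% |
| m = 5, r = 0.1 | 4.5% | 4.8% | 5.5% |
| m = 10, r = 0.1 | 4.4% | 5.1% | 7.1% |
| m = 5, r = 0.2 | 4.1% | 4.4% | 5.1% |
| m = 10, r = 0.2 | 3.7% | 4.5% | 6.6% |

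At q = 0.5 the error first exceeds 5% at m = 4 (r = 0) or m = 9 (r = 0.1).

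**Opposing bias.** Route 3 admits unscanned subjects only as failures. Suppose 5 further subjects are never scanned and half of their failures enter this way.

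| | q = 0.25 | q = 0.5 | q = 1 |
|---|---|---|---|
| m = 5, r = 0 | 3.4% | 3.8% | 4.8% |
| m = 10, r = 0 | 3.8% | 4.8% | 7.1% |
| m = 5, r = 0.1 | 3.3% | 3.8% | 4.7% |
| m = 10, r = 0.1 | 3.6% | 4.4% | 6.3% |

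**Near the threshold.** 82/95 has lower bound 0.791 (goal not met); 82/94 has 0.801 (met). One late-CT subject who is dropped rather than counted as a failure can decide the result.

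**A related mismatch on enlargement.** SAP 2.4.2 counts enlargement "with or without intervention between the baseline and the 12 month analysis window". SAP 5.2 uses the measurement nearest day 365 and sets no window. SAP 4.1, Table 1 also schedules a contrast CT at 6 months. By the ideal windows, that scan lies 365 − 210 = 155 to 365 − 150 = 215 days from day 365. A 24-month scan lies 640 − 365 = 275 to 820 − 365 = 455 days away. So 5.2 would usually pick the 6-month scan for a late-CT subject. By the analysis windows the distances overlap (123 to 275 days, against 182 or more), so the late scan could be picked instead.

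**The case against.** **The rule has a rationale.** A clean later scan is fair evidence that no endoleak or migration was present at 12 months, whereas a late finding may be new. This stands as an explanation. It does not make dropping the subject neutral: the bias is upward whenever q > r. That is likely if 12-month findings tend to persist, but the documents do not establish it.

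**The harm is not shown.** m, q and r are unknown. Once the event clause is allowed for, 10 of the 12 cells in the second table are below 5%. This stands, and it limits the claim to an error rate that is not guaranteed.

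**q = 1 is an extreme.** It requires every 12-month failure to carry a listed finding that persists to the late scan. Technical failure and conversion enter through the event clause, and enlargement is not screened. This stands; read the q = 1 column as an upper bound.

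**The 82/94 example contrasts only with counting the subject as a failure.** The Short Neck rule would drop the same subject. This stands. The difference is that the Short Neck rule also drops late-CT subjects with clean scans, so it does not select on the scan result.

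**Part of the SAP is not visible.** The text of 5.5 before 5.5.5 is not shown and may already hold a sensitivity analysis. That could meet part of the fix, but it would not change the primary population.

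**Conclusion.** The concern holds. As written, entry to the High Neck Angulation effectiveness denominator depends on the result of the late scan for four of the endpoint's components. The error rate stated in SAP 5.4 is therefore not assured for this substudy. The reading of the text is firm; the size is not. In the first table type I error runs from 3.7% to 8.0%, against 4.2% with no late-CT subjects, and it depends on assumed m, q and r at a true rate of 80%. With few late-CT subjects the effect is small, and failures admitted without imaging can offset it. The Short Neck Substudy has no late-CT route and is not affected. This should be fixed.

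**What to change.** Remove the outcome condition from SAP 5.1 in one of two ways:

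- **(a)** Exclude every subject without a contrast CT in days 243 to 546, whatever a later CT shows, unless an eligible 2.4.2 event brings the subject in. This matches the Short Neck rule.
- **(b)** Include every such subject who has a post-window CT, and count a Core Lab Type I or III endoleak, migration or rupture on it as failure. Amend 2.4.2 to match and set a cut-off date for late CTs, since SAP 5.3 sets none.

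Pre-specify one as primary and report the other as a sensitivity analysis, unless the sections not shown already do so. If the primary analysis has been run, report both as sensitivity analyses. Also reconcile 2.4.2 and 5.2 on whether an enlargement measurement outside the 12-month window counts.

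The cost is SAP wording and one table, with no new data. At an assumed true rate of 90%, exact power with 95 subjects is 84.8%.

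- **Under (a)**, power is 81.4% with 90 subjects and 77.2% with 85. Type I error is at most 3.8% and 3.3%. These figures move in steps with n: at n = 94, type I error is 4.7% and power 85.6%. Selection through the event clause remains, but it can only lower the success rate.
- **Under (b)**, a failure arising after the window may be counted as a 12-month failure. If 10% of late-CT successes show a new finding, power is 80.8% at m = 5 and 76.3% at m = 10, and type I error is 3.4% and 2.7%.

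Both keep type I error below 5% in this model.

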5.2 Endpoint Variables

- Death Site reported events.
- Stroke CEC adjudicated site reported events through all follow-up time periods.
- Myocardial Infarction CEC adjudicated site reported events through the 5-year follow-up periods.
- Bowel Ischemia CEC adjudicated site reported events through the 5-year followup periods.
- Paraplegia CEC adjudicated site reported events through the 5-year follow-up periods.
- Respiratory Failure CEC adjudicated site reported events through the 5-year follow-up periods.
- Renal Failure CEC adjudicated site reported events through the 5-year follow-up periods.
- Procedural Blood Loss > 1000 mL Site reported events during initial procedure.
- Thromboembolic events CEC adjudicated site reported events through the 5-year follow-up periods.
- Type I endoleaks Core Lab reported events.
- Type III endoleaks Core Lab reported events.
- Migration Core Lab reported prosthesis or intercomponent migration.
- AAA enlargement Using Core Lab reported data, the measurement closest to 30 days after initial implant will be subtracted from the measurement closest to 365 days after initial implant.
- AAA rupture –Core Lab reported events or CEC adjudicated site reported events through the 5-year follow-up periods.
- Conversion to open repair CEC adjudicated site reported events through the 5vear follow-up periods.
- Aneurysm related mortality CEC adjudicated site reported events through the 5year follow-up periods.
- Stent fracture Core Lab reported events.
- Reintervention CEC adjudicated site reported events through the 5-year follow-up periods.
- Type II endoleak –Core Lab reported events.
- Type IV endoleak –Core Lab reported events.
- Index Procedure Time Site reported during initial procedure.
- Length of Hospital Stay Site reported during initial hospitalization.

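### High Neck late-CT route: a clean scan after the 12 month window is accepted as evidence of 12 month status with no condition that graft and aneurysm were untreated in between

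*SAP*

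**What the plan says.** SAP 5.1 (Primary Effectiveness Population, High Neck Angulation Substudy) normally requires an early post-operative contrast CT and a 12 month contrast CT. If the 12 month scan is missing, a later contrast CT can replace it, provided it is one "at which there was no endpoint event identified by Core Lab (Type I Endoleak, Type III Endoleak, Migration, or Rupture"). The scan to be used is fixed by the words "using the post 12-month contrast CT closest to the 12-month window, the subject will also be included in the analysis". No latest day is given.

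A further sentence, beginning "Additionally, any Subjects with an eligible effectiveness", brings in anyone with an event under SAP 2.4.2, whatever their imaging. The time limits in 2.4.2 are:

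- Endoleak: "Type I endoleaks in the 12 month analysis window", with Type III worded the same way.
- Rupture: "AAA rupture through the 12 month analysis window".
- Conversion: "Conversion to open repair through the 12 month analysis window".

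Table 2 in SAP 4.2 sets the 12 month analysis window at days 243 to 546. Reintervention is a secondary endpoint (SAP 2.4.3) and not a component of the primary one.

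SAP 5.2 takes rupture from two sources, "Core Lab reported events or CEC adjudicated site reported events". It also lists "Reintervention CEC adjudicated site reported events", and conversion is adjudicated too, all through five years.

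**The concern.** Using a late clean scan in place of a missing one rests on an inference: if no endoleak or migration is visible later, none was present at 12 months. That inference needs the graft and aneurysm to have been left alone in the meantime. The route does not ask for this.

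Take a subject with no contrast CT in days 243 to 546, a Type I endoleak present but unseen in that window, an endovascular repair on day 600, and a clean contrast CT on day 700. The route admits the subject. No 2.4.2 event is on record, so absent any other failure the subject is scored a success. The same can follow an open conversion, after which the scan may no longer show the study device, or a rupture that was adjudicated by the Clinical Events Committee (CEC) and repaired but is not visible to the Core Lab later.

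At stake is a primary endpoint tested against a fixed goal. When treatment hides a finding, a failure is scored as a success and never the reverse, so the error can only help the substudy pass.

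**Working it through.** **Step 1. Does any other text close the gap?**

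- Rupture or conversion up to day 546: caught by the event sentence in 5.1, because 2.4.2 counts both to the end of the window.
- Rupture or conversion after day 546: not a 2.4.2 event, so not caught. The late-CT list omits conversion and recognises rupture only if the Core Lab identifies it.
- Reintervention at any time: not a 2.4.2 event and not on the list.
- AAA enlargement: not on the list. It has its own rule in 5.2, using the measurement closest to day 365, which may draw on the same late CT.

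The gap therefore exists for treatment between day 546 and the late CT. The SAP does not define the start of the post-12 month period in days; day 546 is inferred from Table 2.

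**Step 2. How long can the unchecked interval be?** The 24 month window ends on day 911, so with a 24 month scan it is up to 911 − 546 = 365 days. With no latest day for the scan, it could reach the end of the 60 month window: 2006 − 546 = 1460 days.

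**Step 3. The pass mark.** Inputs: goal 0.80 (SAP 2.5.2), one-sided exact Clopper-Pearson with alpha 0.05 (SAP 5.4), n = 95 (SAP 2.7). The lower bound for x successes in n is the 5th percentile of a Beta(x, n − x + 1) distribution.

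- 83/95: bound 0.8034, pass.
- 82/95: bound 0.7913, fail.

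The pass mark is 83, with exact type I error P(X ≥ 83) = 0.0424 for X ~ Binomial(95, 0.80). The choice of 95 cannot be reproduced, since the public text shows no expected rate, power or dropout. This point does not depend on it.

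**Step 4. Effect on type I error.** The number of affected subjects is not in the documents; 0 to 3 is an assumption. All 95 are taken as analysed.

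- Model A: k subjects of unknown status are always scored successes and the other 95 − k succeed with probability 0.80. P(pass) = P(Y ≥ 83 − k), Y ~ Binomial(95 − k, 0.80).
- Model B: k subjects who truly failed at 12 months are scored successes. P(pass) = P(X ≥ 83 − k), X ~ Binomial(95, 0.80).

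| k | Model A | Model B |
|---|---|---|
| 0 | 0.042 | 0.042 |
| 1 | 0.047 | 0.075 |
| 2 | 0.052 | 0.122 |
| 3 | 0.057 | 0.186 |

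Model B is the extreme case: it takes every affected subject to be a hidden failure.

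**Step 5. Can one admitted subject change the result?** Suppose the other routes give 76/87 (bound 0.7994, fail). One more success gives 77/88 (0.8016, pass); one more failure gives 76/88 (0.7884, fail). This is uncommon. For starting sizes 75 to 94, adding one success turns a fail into a pass only at n = 75, 81, 87 and 93, and at each only for one exact count.

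**Step 6. What the fix would do at the margin.** Start from 83/95 with one affected subject scored a success. Leaving that subject out gives 82/94 (0.8014, still a pass). Counting the subject as a failure gives 82/95 (0.7913, fail). With two left out, 81/93 (0.7993) fails.

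**The case against.** Four arguments stand against making much of this.

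1. **The late event is not a one-year failure.** A reader might infer that a subject converted, ruptured or re-treated on day 600 is a failure wrongly scored as a success. The documents do not support that. Section 2.4.2 stops counting rupture and conversion at day 546 and never counts reintervention. A subject with a clean on-time CT and the same day-600 event is also a success. This objection stands in full. What is left is the difference in evidence: the on-time subject's 12 month status was observed, whereas the late-route subject's is inferred from a scan that treatment has made uninformative.

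2. **The choice of scan limits the problem.** The route uses the post-window contrast CT nearest the window. If the scan that prompted the repair was a contrast CT after the window, read by the Core Lab, and showed the finding, it is the scan used and it blocks entry. Masking needs a chain: no contrast CT in a 304-day window (546 − 243 + 1), a finding already present then, no earlier post-window contrast CT showing it, a treatment, and a clean scan afterwards. This stands, and it makes the case rare. It does not make it impossible.

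3. **The numbers are knife-edge.** This largely stands. In Model A one such subject leaves the chance of a false pass at 0.047, still under 0.05. Model B's larger figures need every affected subject to be a true failure, which no passage shows.

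4. **Not all of the plan is visible.** The text of SAP 5.5.1 to 5.5.4 and the protocol body are not in the public material, and a sensitivity analysis may be described there. That is possible, but the entry rule in 5.1 is complete as printed and would still lack the condition.

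**Conclusion.** The point holds in a limited form. The High Neck late-CT route treats a scan after day 546 as evidence of 12 month status without requiring that no rupture, conversion or relevant reintervention came between. Where one did, 12 month status is unknown, yet the subject enters as a success, and any misclassification favours passing the 80% goal.

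It would be wrong to conclude that events after day 546 are themselves misclassified failures, or that one such subject would usually decide the substudy. One subject matters only for a result at the margin, such as exactly 83 of 95.

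The conclusion rests on day 546 as the end of the 12 month window, on the exact test in SAP 5.4, and on an assumed handful of affected subjects that the documents neither give nor allow to be estimated. Severity is minor; it is a cheap improvement.

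**What to change.** In the High Neck late-CT sentence of SAP 5.1, add a condition: the late CT may be used only if, after the 12 month window and before that CT, there was no AAA rupture (from either source in 5.2), no conversion to open repair, and no reintervention for Type I or III endoleak, migration or AAA enlargement. If one occurred, treat 12 month status as not observed, and do not let the subject enter as a success by this route.

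Leaving these subjects out may itself be informative, so report a sensitivity analysis that counts them as failures, and state how many there are.

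Do not make events after day 546 primary failures. That would score two subjects with the same late event in opposite ways, depending only on whether the 12 month CT was done. It would also turn reintervention into a primary component, against 2.4.2.

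The cost is a short addition to the SAP and one extra analysis. No new data are needed, because rupture, conversion and reintervention are already adjudicated through five years. The downside is a slightly smaller analysis set and a possibly less favourable reported rate.
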